5.5.1. Definition of Endpoint(s)

5.5.1.1. Psoriasis Area and Severity Index (PASI)

The Psoriasis Area and Severity Index (PASI) is an instrument used for assessing and grading the severity of psoriatic lesions and their response to therapy. In the PASI system, the body is divided into 4 regions: the head, trunk, upper extremities, and lower extremities. Each of these areas is assessed separately for erythema, induration and scaling, which are each rated on a scale of 0 to 4. The PASI produces a numeric score that can range from 0 (no psoriasis) to 72. A higher score indicates a more severe disease.

5.5.2. Estimand(s)

Not applicable for the re-treatment analysis.

5.5.3. Analysis Methods

5.5.3.1. Psoriasis Area and Severity Index (PASI)

- Proportion of subjects who regain control of disease (PASI <3) 24 weeks after start of re-treatment

The proportion of subjects showing a PASI value <3 within the R24 visit window will be displayed in a frequency table providing the number and percentage of subjects per analysis group and overall (NRI and OC analysis). For all proportions, unstratified two-sided 95% confidence intervals (CIs) according to Clopper-Pearson will be calculated. Graphical presentation will be done by means of bar charts.

Details on handling of missing data are described in section 5.1.8. For the analysis groups III to V (total only), subgroup analyses will be performed as specified in section 5.8.8. Subgroups will be compared exploratorily for the NRI analysis using the Chi-square test (without covariate) to test the difference between two subgroups. The 95% confidence interval for the difference will be calculated based on the Wald statistic. Counts and percentages for subjects responding to treatment, along with odds ratio (OR), relative risk (RR) and risk difference (RD), 95% confidence intervals and the nominal (not adjusted for multiplicity) p-value for the factor effect 'subgroup' will be provided. Graphical presentation will be done by means of bar charts.

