11.8. Other Analyses

Stratified Newcombe confidence limits for the common proportion difference with respect to the primary endpoint will also be provided by using the method of Yan and Su ([Yan und Su 2010](#)).

In addition, the primary endpoint will also be analyzed without adjustment for disease duration ('unadjusted analysis'). The two-group large-sample normal approximation Z-test ('asymptotic

Wald test of noninferiority') along with the two-sided 90% Wald type and Newcombe confidence interval will be computed.

For binary endpoints in Study Part 2 counts and percentage of subjects per treatment group along with odds ratio (OR), relative risk (RR) and risk difference (RD), two-sided 90% confidence intervals and p-values for treatment comparison based on Mantel-Haenszel weights adjusted for disease duration will be provided.

The change from baseline of continuous endpoints in Study Part 2 will be analyzed by an analysis of covariance model (ANCOVA) with the fixed effect factors for treatment group and disease duration and the baseline value as covariate. The Least-Squares means (LS means), the LS mean difference and the standardized mean difference (computed according to Hedges' g) with the two-sided 90% CI will be provided from the ANCOVA model.

Statistical analyses for time to event endpoints in Study Part 2 will provide the median time-to-even estimates per treatment group with two-sided 90% confidence intervals and the hazard ratio (including two-sided 90% confidence interval) calculated from Cox-regression with the factors treatment group and disease duration as covariate.

Exploration of possible heterogeneity of treatment effects across centers for the primary endpoint will be performed by descriptive frequency statistics including graphical display of the results of the individual centers, as appropriate. No pooling of centers will be performed.

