5.1.8. Missing Data Imputation

Data of efficacy endpoints from subjects who started a protocol-prohibited medication/therapy during the study that could improve psoriasis will be set to 'missing' from that point onward. If the prohibited medication was stopped and the stop date is before the R0 visit, any efficacy data observed on or after the R0 visit will be used for analysis. The protocol-prohibited medications/therapies are listed in section 8.1 of the CSP. For the statistical analysis of the Re-treatment phase, protocol prohibited medication/therapy will be identified in the SDTM DV domain as DVDECOD='Received a disallowed concomitant treatment'.

After the rule for handling of protocol-prohibited medication/therapy is applied, missing data will be handled as follows:

- Non-responder imputation for binary efficacy endpoints will be applied for subjects with missing data within a given visit window.
- Last Observation Carried Forward (LOCF) imputation for continuous efficacy endpoints will be applied for subjects with missing data in the Re-treatment phase. Only the visits R8, R16, and R24, or any unscheduled visit after R0, will be considered as the LOCF value.
 - This approach implies that a separate "endpoint" visit will be calculated that gets the imputed value, thus leaving the observed value as it is, if data are summarized descriptively only.
- Time-to-event analyses of binary endpoints will be performed after the rule for handling of protocol-prohibited medication/therapy is applied (missing data will not be replaced for time-to-event analyses).

An 'observed cases analysis' for all binary and continuous endpoints in the Re-treatment phase without any imputation of missing data (ie, also not set to missing once protocol-prohibited medication/therapy is started) will also be done. These analyses will provide only descriptive statistical results (see section 5.6).

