4. POPULATIONS (ANALYSIS SETS) FOR THE OVERALL SAFETY ANALYSIS

In the Overall safety analysis, the following analysis sets will be defined.

4.1. All Subjects Treated in Study Part 1

880 subjects started open-label guselkumab in Study Part 1 and received at least one dose (study group **1**). All 880 subjects are included in this analysis set to be evaluated for AEs in the study period from date of first dose (week 0) until the day before the date of the week 28 dose (start of randomized or open-label treatment within Study Part 2), or, in 58 subjects not starting Study Part 2, until the end of documentation.

4.2. All Subjects Treated in Study Part 2

From all 880 subjects who started open-label guselkumab in Study Part 1, 297 super-responders received randomized treatment in Study Part 2 (study groups **2a** and **2b**) and 525 non-super-responders continued open-label treatment (study group **2c**). So, 822 subjects are included in this analysis set and will be displayed separately to be evaluated for AEs in the study period from date

of the first verum dose (week 28 or week 36) until date of last verum dose (week 52 or week 60) in Study Part 2 plus 90 days (date of re-treatment and thereafter excluded, if at all).

4.3. All Subjects Randomized for Study Part 2

Among the 297 super-responders treated in Study Part 2 (study groups **2a** and **2b**), 148 were randomized to guselkumab q8w and 149 to guselkumab q16w. The 297 subjects included in this analysis set will be evaluated and displayed separately for AEs in the study period from date of randomization (week 28) until date of last verum dose (week 52 or week 60) in Part 2 plus 90 days (date of re-treatment and thereafter excluded, if at all).

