4.5. All Subjects who Started Re-Treatment

From all 273 subjects starting the Withdrawal phase after the week 68 visit (randomized subjects only), those 227 subjects will be selected who started re-treatment with open-label guselkumab for additional up to 3 doses after showing PASI deterioration of > 5 until the week 220 visit. In addition, 9 subjects started re-treatment without a Withdrawal phase (among these, 3 subjects who started re-treatment during Study Part 2 (before the week 68 visit) with PASI > 5, and 6 subjects who started re-treatment at the week 68 visit with a PASI value of 3 to 5) and will be included as well. The 236 subjects included in this analysis set will be evaluated for AEs starting from the date of re-treatment until the end of documentation.

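### Subgroup risk differences in the re-treatment analysis carry only a Wald 95% interval, which can cover well below 95% if a subgroup is small, the split is unequal and response is high

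*SAP*

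**What the plan says.** The Re-treatment SAP compares subgroups, within the total of analysis groups III to V, on one protocol-defined endpoint: "Proportion of subjects who regain control of disease (PASI <3) 24 weeks after start of re-treatment". Section 5.5.3.1 sets three methods:

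- Single proportions: "For all proportions, unstratified two-sided 95% confidence intervals (CIs) according to Clopper-Pearson will be calculated".
- Test: "Subgroups will be compared exploratorily for the NRI analysis using the Chi-square test (without covariate) to test the difference between two subgroups".
- Difference: "The 95% confidence interval for the difference will be calculated based on the Wald statistic".

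Section 5.6.1 repeats this for PASI 0, ≤1 and ≤5 at R24, and section 5.6.3 for the two DLQI response criteria. None of the three sections has a fallback for sparse or 100% cells.

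The general section 5.1 describes the binary test differently, as a two-group chi-square test according to Wald.

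The comparison uses non-responder imputation (5.1.8): "Non-responder imputation for binary efficacy endpoints will be applied for subjects with missing data within a given visit window". Values after prohibited therapy are set to missing first, so they also count as non-response.

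Protocol 11.8 treats the primary endpoint differently: "Stratified Newcombe confidence limits for the common proportion difference with respect to the primary endpoint will also be provided". Its unadjusted analysis there also pairs a Wald-type interval with a Newcombe interval.

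**The concern.** The Wald interval estimates its variance from the observed proportions. When response is high and one subgroup is small, that subgroup often shows few or no failures, its variance term shrinks towards zero, and the interval is too short and badly placed.

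Both conditions are plausible here. Every re-treated subject had PASI 0 at weeks 20 and 28 on the same drug, so high rates of PASI <3 and ≤5 would not be surprising. Several subgroup factors in 5.8.8 are not balanced by design: the four entry-time levels of D, the three BMI classes of E, and M, which splits only the short-duration subjects. The single proportions get exact limits and the primary endpoint gets Newcombe limits, while these smaller comparisons get Wald alone.

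At stake is whether an interval labelled 95% in an exploratory table suggests a subgroup difference in regaining control that the data do not support.

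**Working it through.** **Plan's own figure.** There is none for this analysis beyond the nominal 95%.

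**Inputs from the documents.** Overall safety SAP 4.5: "those 227 subjects will be selected who started re-treatment with open-label guselkumab for additional up to 3 doses". A further 9 had no withdrawal phase (227 + 9 = 236). The comparisons concern the 227. Subgroup A descends from near-equal randomization ("148 were randomized to guselkumab q8w and 149 to guselkumab q16w"). J and K are median splits, so about 114:113, ties aside.

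**Assumed inputs.** Sizes of D, E and M, and the R24 rate, are not stated. I used illustrative splits of 227 and true rates of 90%, 95% and 98%, equal in both subgroups. The only planning figure in the documents for PASI <3 is 90%, on q8w at week 68 (protocol 11.2).

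**Formulas.** With d = p1 − p2 and Wilson limits (l, u) for each proportion:

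- Wald: d ± 1.96 × √[p1(1−p1)/n1 + p2(1−p2)/n2]
- Newcombe lower: d − √[(p1−l1)² + (u2−p2)²]
- Newcombe upper: d + √[(u1−p1)² + (p2−l2)²]

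Coverage is the sum of the joint binomial probabilities of all outcomes whose interval contains the true difference.

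**Exact coverage, Wald / Newcombe (%)**

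| Split | 90% | 95% | 98% |
|---|---|---|---|
| 114:113 | 94.7 / 95.3 | 94.9 / 96.2 | 95.7 / 98.0 |
| 170:57 | 93.9 / 95.4 | 91.6 / 96.0 | 85.7 / 97.0 |
| 187:40 | 91.7 / 95.2 | 86.5 / 96.3 | 76.9 / 95.9 |
| 197:30 | 90.3 / 95.8 | 78.3 / 96.2 | 69.5 / 95.8 |
| 207:20 | 87.1 / 96.0 | 64.2 / 95.6 | 60.2 / 95.7 |

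A comparison of two levels of a multi-level factor uses fewer than 227 subjects: 100:20 at 95% gives 73.1 / 96.5. Equal small groups with equal rates do not under-cover (30:30 at 95%: Wald 97.2%), but with unequal rates they can (30:30 at 95% against 99%: 78.3%).

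**One subgroup at 100%: 187/197 against 30/30.** d = 0.9492 − 1 = −0.0508.

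- Wald: standard error = √(0.9492 × 0.0508/197 + 0) = 0.0156; −0.0508 ± 0.0307 gives −8.1 to −2.0 points, excluding 0.
- Wilson limits: 0.9091 to 0.9722, and 0.8865 to 1.
- Newcombe lower: −0.0508 − √(0.0401² + 0²) = −0.091. Upper: −0.0508 + √(0.0230² + 0.1135²) = +0.065. The interval includes 0.
- Wald p = 0.001; Pearson chi-square p = 0.21; Fisher p = 0.37.

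If the true rate is 95%, a subgroup of 30 reaches 30/30 with probability 0.95³⁰ = 0.215.

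**Zero width.** This needs both subgroups at 0% or both at 100%, or one at each. For all 227 in two groups at a common rate, the probability that everyone responds is 0.98²²⁷ = 1.0% at 98% and 0.99²²⁷ = 10.2% at 99%. For 45:45 at 98% it is 0.98⁹⁰ = 16.2%.

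**The case against.** The strongest reply is that the harm rests on two inputs the documents do not give. A reader might infer that the subgroups are in fact small and unequal and that response is near 100%. The documents do not support either as fact. J and K are about 114:113 and A descends from 148:149. C and G were excluded from inference and then dropped, and I has no comparison. Non-responder imputation lowers the analysed rate, and nothing shows that PASI 0, PASI ≤1 or the DLQI criteria are near a boundary. This stands, and it makes the conclusion conditional.

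A reader might also infer that intervals will often collapse to zero width. For a two-way split of all 227 that is unlikely unless the rate is about 99%. In the 45:45 case at 98%, Wald coverage is a conservative 99.0%, and an interval from 0 to 0 cannot suggest a difference.

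A third inference would be that the p-values are inflated too. If 5.5.3.1 means a Pearson chi-square test, its true size at 187:40 is 3.8% at 95% response and 4.9% at 98%, so broadly it is not. It rises above 5% only at extreme rates (207:20 at 99%: 8.0%). If the wording in 5.1 governs, the p-value shares the interval's defect. The SAP leaves this open.

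Finally, the analysis is exploratory with nominal p-values, the exact limits and counts let a reader spot a 100% cell, and the protocol adds Newcombe to Wald rather than replacing it. These points limit the stakes. They do not justify labelling an interval 95% when it may cover much less.

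**Conclusion.** The point holds conditionally. If a subgroup has about 40 or fewer subjects in an unequal split and the imputed response rate is about 90% or higher, the Wald interval covers less than its label says. Over the 187:40 to 207:20 splits, coverage is 87.1% to 91.7% at 90% response and 64.2% to 86.5% at 95%. A single subgroup at 100% can make it exclude zero when a score interval does not. D, E and M are the factors where this could happen.

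The subgroup sizes and R24 rates are assumptions. At 80% response the shortfall is smaller (187:40 gives 93.7%). Near-balanced splits such as J and K need no correction. The confirmatory non-inferiority conclusion is untouched. This is a cheap improvement to exploratory tables.

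**What to change.** In Re-treatment SAP 5.5.3.1, 5.6.1 and 5.6.3, replace the Wald interval for the risk difference by the Newcombe hybrid score interval. It is already in protocol 11.8 and never has zero width: with 197/197 and 30/30 it gives −1.9 to +11.4 points where Wald gives 0 to 0.

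State that the subgroup p-value comes from the Pearson chi-square test, and align 5.1 with those three sections. Fisher's exact test for sparse tables is optional.

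The cost is a change of interval option and three amended sentences, plus the wording in 5.1. Balanced splits change little. The downside is that some exploratory intervals become wider. With a subgroup as small as 10 of 227, Newcombe coverage itself ranges from 92.0% to 96.3% over the rates examined (80% to 99%), so very small levels should still be read with caution.

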5.6. Additional Analyses

New analyses that were not pre-planned in the CSP are introduced as follows:

5.6.1. PASI Assessments

Efficacy parameters related to the PASI score are defined below:

Time to regain disease control after start of re-treatment

The time to regain disease control is defined as time from the R0 visit (planned start of re-treatment) to first date PASI is <3 within the Re-treatment phase. In the absence of documented disease control the time to regain disease control will be censored at the date of the last PASI assessment until the week R24 visit. The time to regain disease control will be computed as:

- Date of PASI <3 – Date of week R0, if the subject regains disease control,
- Date of last PASI assessment – Date of week R0, if the subject does not regain disease control.

The following endpoints will be evaluated:

- Time to regain disease control (PASI <3) after start of re-treatment

The time to regain disease control will be analyzed using the Kaplan-Meier product limit method. Summary tables will provide counts and percentages by analysis group and overall, the median time-to-event with 95% CIs. The analysis will be performed on the observed cases only after the rule for handling of protocol-prohibited medication/therapy is applied. (ie, missing data will not be replaced for time-to-event analyses). Time to regain disease control will also be computed for subgroups (for the total only of analysis groups III to V), and subgroups will be compared using the log-rank test. The survival curves will also be displayed graphically: by analysis group and by subgroups.

Update after the Dry Run Meeting for the first interim analysis: The Kaplan-Meier analysis will not be performed on observed cases but as NRI analysis as PASI values under prohibited medication will not be used for analysis.

Update before start of programming for the final week 220 analysis: To harmonize with the statistical analysis for the Withdrawal phase, the Kaplan-Meier analysis will be performed on observed cases (OC) while PASI values under prohibited medication will not be used for analysis.

- Proportion of subjects who achieve a PASI value =0 over time
- Proportion of subjects who achieve a PASI value ≤ 1 over time
- Proportion of subjects who achieve a PASI value <3 over time
- Proportion of subjects who achieve a PASI value ≤ 5 over time

Per analysis group and overall, the proportion of subjects meeting the response criterion will be displayed in a frequency table providing the number and percentage of subjects (NRI analysis). No inferential statistics will be provided. Graphical presentation will be done by means of bar charts. For the analysis groups III to V (total only), subgroup analyses will be performed as specified in section 5.8.8.

- Proportion of subjects with PASI value =0 at 24 weeks after start of re-treatment
- Proportion of subjects with PASI value ≤ 1 at 24 weeks after start of re-treatment
- Proportion of subjects with PASI value ≤ 5 at 24 weeks after start of re-treatment

These endpoints will be analyzed for subgroups within analysis groups III to V (total only). The proportion of subjects showing response within the R24 visit window will be displayed in a frequency table providing the number and percentage of subjects per subgroup (NRI analysis). For all proportions, unstratified two-sided 95% confidence intervals (CIs) according to Clopper-Pearson will be calculated. Subgroups will be compared exploratorily for the NRI analysis using the Chi-square test (without covariate) to test the difference between two subgroups. The 95% confidence interval for the difference will be calculated based on the Wald statistic. Counts and percentages for subjects responding to treatment, along with odds ratio (OR), relative risk (RR) and risk difference (RD), 95% confidence intervals and the nominal (not adjusted for multiplicity) p-value for the factor effect 'subgroup' will be provided.

- PASI values over time

Per analysis group and overall, PASI values at scheduled study visits and changes from baseline (R0 visit) will be tabulated by descriptive statistics (OC analysis). No inferential statistics will be provided. For the analysis groups III to V (total only), subgroup analyses will be performed as specified in section 5.8.8.

- Change from baseline (R0 visit) in PASI value 24 weeks after start of re-treatment

The change from baseline (R0 visit) to week R24 will be tabulated for all subjects of analysis groups III to V (total only). A univariate ANCOVA model will be used to test the difference between subgroups; the change from baseline being the dependent variable, and subgroup and baseline as independent variables. A 95% confidence interval for the difference in Least Squares (LS) means and nominal (not adjusted for multiplicity) p-value will be calculated based on contrast test statistics. The LS means, the LS mean difference and the standardized mean difference (computed according to Hedges' g), together with the 95% CI and two-sided nominal p-value, will be provided from the ANCOVA model.

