5.1.1. Visit Windows

As subjects do not always adhere to the protocol visit schedule, the following rules are applied to assign actual visits to analysis visits. Listed below are the visit windows for analysis and the target days for each visit. The reference day is Re-treatment Day 1 (for definition see section 5.1.3). If a subject has two or more actual visits in one visit window, the visit closest to the target day will be used as the protocol visit for that visit window. Additional or unscheduled visits will not be used in the summaries or analyses, but they can be used for determination of clinically important endpoints. If two actual visits are equidistant from the target day within a visit window, the later visit will be used.

Study visits of Study Parts 1, 2 and 3 taken place before re-treatment with guselkumab has been started will not be re-assigned to visit windows as they will not be included in tabulation; however, the (negative) relative day will be computed to be displayed in the individual data listings.

All assignments will be made in chronological order. Once a visit date is assigned to a visit window, it will no longer be used for a later time point except for the endpoint. Listed below in Table 2 are the visit windows and the target days for each visit of the Re-treatment phase.

Table 2 – Visit Windows for Analysis

Parameter	Analysis Period	Scheduled Visit	Time Interval (Label on output)	Time Interval (Day) *	Target Time Point (Day)
All	Re-trt	R0	Week R0	Not applicable #	1
		R8	Week R8	20 to 85	57
		R16	Week R16	86 to 127	113
		R24	Week R24	> 127	169
		R28	Week R28 (SFU)	Not applicable&	197

* Relative to Re-treatment Day 1. Time intervals for analysis are wider than the visit windows allowed per CSP.

In some subjects, the first re-treatment dose was given at an unscheduled visit after the R0 visit. For these, the R0 visit will have a negative relative day.

& No visit window is defined for the safety follow-up visit as no efficacy data are obtained at this visit.

If there are site visits outside of the defined windows above, final decisions on the allocation of the actual visit to an earlier or later planned visit or whether the data will not be included in the analysis will be made during the Data Review or Dry Run Meeting.

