5.6.2. End of the Treatment-Free Period

- Time to end of the treatment-free period

The time to end of the treatment-free period is defined as time from the visit guselkumab was injected the last time in Study Part 2 to the date of the R0 visit at which re-treatment was to start, irrespective of PASI assessments. No censoring for subjects without re-treatment applies, as only subjects starting re-treatment are included in the analysis. The time to end of the treatment-free period will be computed as:

- Date of R0 visit – Date of last guselkumab injection in Study Part 2.

The time to end of the treatment-free period will be displayed for observed cases in a summary table providing the mean and median time-to-event, by analysis group and overall. No inferential statistics will be provided.

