5.7.2. Adverse Events

The verbatim terms used in the eCRF by investigators to describe adverse events will be coded using the Medical Dictionary for Regulatory Activities (MedDRA). Any AE occurring at or after the day of first re-treatment dose is considered to be treatment-emergent. If the onset date is recorded partially only or is completely missing, then the event is regarded as treatment-emergent unless it is known to be prior to the first dose of re-treatment based on partial onset date or

resolution date. All reported treatment-emergent adverse events (TEAEs) will be included in the detailed analysis.

For each adverse event (ie, Preferred Term) the number and percentage of subjects who experience at least one occurrence of the given event will be provided. Summary tabulation will also provide the number of events, if applicable.

Summary tables will be generated for:

- AEs
- TEAEs
- TEAEs by severity
- TEAEs by relationship to study agent
- TEAEs leading to discontinuation of study agent
- Infections
- Injection site reactions
- Serious TEAEs (TESAEs)
- Serious infections
- Serious injection site reactions.

In addition to the summary tables, listings will be provided for subjects who:

- Had (S)AEs
- Had AEs leading to discontinuation of study agent.

Deaths will be displayed by analysis group. Frequencies for the following parameters will be included in the summary table:

- Number of subjects who died
- Cause of death
- Relationship to study agent (yes/no) (yes includes the following eCRF items: possible, probable, very likely).

A listing of subjects who died will also be provided.

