5.7.2. Adverse Events

The verbatim terms used in the eCRF by investigators to describe adverse events will be coded using the Medical Dictionary for Regulatory Activities (MedDRA). Any AE occurring after the day of the week 68 visit until the day of the week 116/164/220 visit (or the R0 visit, if applicable) in Study Part 3 will be included in the analysis. If the onset date is recorded partially only or is completely missing, then the event will be considered for analysis unless it is known to be prior to the week 68 visit based on partial onset date or resolution date. In case a subject missed the week 68 visit, the date of the week 68 visit will be estimated as 8 weeks (56 days) after the week 60 visit.

For each adverse event, the number and percentage of subjects who experience at least one occurrence of the given event will be summarized by study group and overall. Summary tabulation will also provide the number of events, if applicable.

Summary tables will be provided for:

- AEs
- Serious AEs (SAEs)
- AEs by severity
- AEs by relationship to study agent
- Infections
- Serious infections
- Injection site reactions.

In addition to the summary tables, listings will be provided for subjects who:

- Had (S)AEs.

Deaths will be displayed by study group. Frequencies for the following parameters will be included in the summary table:

- Number of subjects who died
- Cause of death
- Relationship to study agent (yes/no) (yes includes the following eCRF items: possible, probable, very likely).

A listing of subjects who died will also be provided.

Any AE occurring after the day of the week 68 visit until the day of the week 116/164/220 visit (or the day before the R0 visit, if applicable, ie, the day of the R0 visit is excluded) in Study Part 3 will be included in the analysis.

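### Re-treatment and Part 3 SAPs: the treatment-free period ends, and time to regain control starts, at the R0 visit, although some subjects were first dosed later

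*SAP*

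**What the plan says.** The protocol (3.1, 9.1.6) has re-treatment begin at the visit where control is lost. The re-treatment SAP records a departure in the footnote to Table 2 (5.1.1): "In some subjects, the first re-treatment dose was given at an unscheduled visit after the R0 visit". It adds that R0 then carries a negative relative day.

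The first re-treatment dose is the origin for:

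- relative days (re-treatment SAP 5.1.3);
- the R8, R16 and R24 windows (5.1.1), and so the PASI <3 proportion at R24 (5.5.3.1);
- treatment-emergent adverse events (5.7.2): "Any AE occurring at or after the day of first re-treatment dose is considered to be treatment-emergent".

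The R0 visit is the reference date for:

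- the endpoint titled "Time to regain disease control (PASI <3) after start of re-treatment" (5.6.1), defined as follows: "The time to regain disease control is defined as time from the R0 visit (planned start of re-treatment) to first date PASI is <3". It is computed as "Date of PASI <3 – Date of week R0, if the subject regains disease control" and, for censored subjects, "Date of last PASI assessment – Date of week R0, if the subject does not regain disease control";
- the end of the treatment-free period (5.6.2), which runs "to the date of the R0 visit at which re-treatment was to start, irrespective of PASI assessments". Part 3 SAP 5.6 uses the same end date;
- the end of the Part 3 adverse-event period (Part 3 SAP 5.7.2), which stops at "the day before the R0 visit, if applicable, ie, the day of the R0 visit is excluded". Part 3 SAP Appendix 2 lists this as a deliberate change.

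**The concern.** A subject who is not dosed at R0 stays untreated until the injection. For that subject, a treatment-free period that stops at R0 does not measure what its name says. A regain time that starts at R0 counts drug-free days as time after the start of re-treatment, which the SAP itself dates to the first dose. The event is the first PASI <3 from R0 within the re-treatment phase, with no condition that a dose has been given, so a low score seen before any injection would count as regained control.

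At stake are the Kaplan-Meier medians for regaining control, the descriptive treatment-free times in the re-treatment SAP, the Kaplan-Meier and Cox analysis of treatment-free time in the Part 3 SAP, and the completeness of the phase-by-phase adverse-event tables. No section reconciles the two dates, reports the delays or plans a sensitivity analysis.

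**Working it through.** **1. The SAP's own clock.** With Day 1 at first dose and no Day 0, target day = 7 × week + 1. Weeks 8, 16, 24 and 28 give 57, 113, 169 and 197, exactly as in Table 2. The windows therefore do run from first dose.

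**2. The identity.** Let g = date of first re-treatment dose − date of R0.

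- Regain time in the SAP = time from first dose + g, for events and for censored subjects.
- Treatment-free time in the SAP = time to first re-treatment dose − g.

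Subjects dosed at R0 have g = 0 and do not change.

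**3. One delayed subject.** The documents do not give g; 7, 14 and 28 days are assumptions.

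- PASI <3 first seen 56 days after first dose: recorded as 56 + g = 63, 70 or 84 days, an excess of 7/56 = 12.5%, 14/56 = 25% or 28/56 = 50%. This lets later visits move with the dose. If visits stay on the R0 calendar, the SAP records 56 days and the first-dose time is 49, 42 or 28 days. The difference is g either way.
- Treatment-free time, q8w subject, last dose at week 60 and R0 at week 80: the SAP records 20 × 7 = 140 days. The time to the injection is 147, 154 or 168 days.

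**4. Group level.** Mean shift = share delayed × g. With 5% delayed by 14 days it is 0.05 × 14 = 0.7 days; with 20% delayed by 28 days it is 0.20 × 28 = 5.6 days. An illustrative simulation placed regain at 56 or 112 days (±7), with 40%, 60% or 80% at the earlier visit, and delayed 5% or 20% of subjects by 14 days:

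| Regain at first visit | Median, no delay | 5% delayed | 20% delayed |
|---|---|---|---|
| 40% | 107 | 107 | 108 |
| 60% | 61 | 62 | 65 |
| 80% | 58 | 58 | 60 |

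The median moves by 0 to 4 days under these assumptions.

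**5. R24 proportion.** The R24 window is any day after 127. A week-24 visit on the R0 calendar falls on relative day 169 − g, which stays above 127 for g up to 41. At g = 28 it is day 141. If visits move with the dose, they fall on target. The same assessment is used in both cases.

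**6. Adverse events.** Part 3 counting ends the day before R0. Re-treatment SAP 5.1 excludes safety data from before re-treatment, and treatment-emergent events start on the dose day. The days from R0 to the day before first dose, g days in all, are in neither summary. Overall safety SAP 4.4 runs to the day before re-treatment starts and so includes them.

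**The case against.** R0 is a disclosed and defensible origin for time to regain control. The SAP calls it the planned start, baseline is the R0 observation (5.1.4), and the protocol counts re-treatment weeks from the date control was lost (2.1.2). Time from the decision to re-treat is a legitimate quantity. This stands, and it means that relabelling is an acceptable remedy for that endpoint. It does not rescue a treatment-free period that ends while the subject is still untreated.

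The stakes are modest. Both time measures are exploratory additions that the protocol did not plan, and both shifts go against the drug: slower regain and a shorter treatment-free time. No favourable claim is inflated. This also stands.

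Some stronger readings are tempting, and the documents do not support them:

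- A reader might infer that the R24 responder rate and the Kaplan-Meier curve cannot be read together. The windows are wide enough that gaps of 7 to 28 days leave the R24 assessment unchanged.
- A reader might infer that the subgroup log-rank tests are biased. Delay distorts them mainly if its frequency or length differs between subgroups, and nothing in the documents says that it does.
- A reader might take 12.5% to 50% as the error in the median. Those figures describe one hypothetical delayed subject.
- A reader might infer that adverse events are lost. They are missing from the two phase summaries only. The overall safety analysis counts them, and the re-treatment SAP's individual listings include data from Parts 1 to 3.

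**Conclusion.** The mismatch is in the text and gives wrong values for late-dosed subjects if the rules are followed as written. It is clearest for the treatment-free period and for the gap between the two adverse-event periods. For time to regain control it is a mismatch between the endpoint's name and its origin, with a loophole for a PASI <3 seen before any dose; the documents do not say whether that happened.

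The error per delayed subject is exactly the R0-to-dose gap. Its effect on group results is unknown because neither the number delayed nor the gap is given. Under the assumed ranges it is small: a mean shift of 0.7 to 5.6 days and a median shift of 0 to 4 days. The primary endpoint is untouched and the R24 proportion essentially so. The point merits correction because the remedy is cheap, not because it threatens a main conclusion.

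**What to change.** - **Treatment-free period** (re-treatment SAP 5.6.2 and Part 3 SAP 5.6): end it at the date of the first re-treatment injection.
- **Adverse events** (Part 3 SAP 5.7.2): run the period to the day before the first re-treatment dose, the rule that overall safety SAP 4.4 already uses.
- **Time to regain control** (re-treatment SAP 5.6.1): measure it from the first re-treatment injection, for events and censored times, and count only a PASI <3 seen after that injection. Alternatively, keep R0, rename the endpoint as time from the R0 visit, and add the first-dose version as a sensitivity analysis.
- **Reporting:** give the number of subjects first dosed after R0 and the distribution of their gap.

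The cost is SAP wording and one date variable, since administration dates are already recorded. The drawback is comparability. The overall safety SAP describes interim analyses of both phases as already performed, so the values for affected subjects will differ from those outputs by their gap. That needs a footnote or a re-run. The overall safety SAP also describes the week 220 analyses in the past tense; if those outputs are final, a supplementary table would serve.
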